5.10.1.1 Required Concomitant medications

Pre-medications on days that Elotuzumab is administered

Dexamethasone- 28 mg PO 3-24 hours prior to Elotuzumab dose

Dexamethasone 8 mg IV 45-90 min prior to Elotuzumab dose

H₁blocker; diphenhydramine (25-50 mg PO/IV) 45-90 min prior to Elotuzumab dose

H₂blocker; Ranitidine or equivalent H₂ blocker (50 mg IV or 150 mg PO), 45-90 min prior to Elotuzumab dose

Acetaminophen 650-1000 mg PO 45-90 min prior to Elotuzumab dose

Anticoagulant Prophylaxis

Aspirin (or other anticoagulant or antiplatelet medication such as clopidogrel bisulfate, low-molecular-weight heparin, or warfarin or factor X inhibitors), is a required concomitant medication while taking lenalidomide. In subjects with a prior history of deep vein thrombosis, low-molecular-weight heparin or therapeutic doses of warfarin (for a target international normalized ratio of 2–3) are required. Enteric-coated aspirin once-daily by mouth at the standard prophylactic dose should be administered for the duration of treatment with lenalidomide. Subjects with known high thrombotic risk, e.g., prior deep vein thrombosis, should receive full anticoagulation at the investigator's discretion

Contraception

Females of childbearing potential (FCBP) must:

- Avoid pregnancy for at least 4 weeks before beginning lenalidomide
- Have a negative pregnancy test within 7 days prior to starting treatment, and each subsequent cycle.
- Pregnancy tests monthly during treatment after the first month or semimonthly for women of childbearing potential with irregular menstruation
- Agree to abstain from heterosexual sexual intercourse or to use 2 methods of effective contraception beginning 4 weeks prior to initiating treatment with lenalidomide, during therapy, during dose interruptions and for 3 months following last dose of drug (more frequent pregnancy tests may be conducted if required per local regulations) An FCBP is defined as a sexually mature female who: 1) has not undergone a hysterectomy or bilateral oophorectomy, or 2) has not been naturally postmenopausal for at least 24 consecutive months (i.e., no menses at any time in the preceding 24 consecutive months). Amenorrhea following cancer therapy does not rule out childbearing potential.

Male subjects and their partners must use 1 highly effective method of birth control plus 1 additional effective method of birth control (contraception) at the SAME TIME during treatment and for 3 months following the last dose of drug, even if they have undergone a successful vasectomy. Male subjects must not donate sperm while taking lenalidomide and for 28 days after stopping lenalidomide.

Highly effective methods of contraception include:

- Intrauterine device (IUD)
- Hormonal therapy (birth control pills, injections, implants)
- Tubal ligation
- Vasectomy

Additional effective methods include:

- Latex condom
- Diaphragm
- Cervical Cap

5.11 Treatment compliance

Records of study medication used, dosages administered, and intervals between visits will be recorded during the study.

6 Visit schedule and assessments**6.1 Visit schedule****Table 6-1****Evaluation and visit schedule**

Assessment	Screening 0-28 days	Day 1 Cycles 1- 2	Day 8	Day 15	Day 22	Day 1 Cycle 3 - beyond	End of Study
Assessment	Screening 0-28 days	Day 1 Cycle 1&2 +/- 3 days	Day 8	Day 15	Day 22	Day 1 C3- beyond +/- 3 days	End Of Study
Informed Consent	X						
Inclusion/exclusion criteria	X						
Vital signs, Physical examination and ECOG Performance Score ⁶	X	X				X	X
Concomitant medications ⁶	X	X				X	X
CBC + diff ⁶	X	X	X	X	X	X	X
CMP ⁶ ,Pregnancy Test ⁶	X	X	X	X	X	X	X
SPEP/UPEP ⁸ /immunofixation	X	X				X	X
Serum free light chains	X	X				X	X
Quantitative immunoglobulins	X	X				X	X
Skeletal survey ³	X					X ³	X ³
Bone marrow asp and bx with Cytogenetics, MM Fish Panel Lab correlative studies ¹		X ¹	X ¹				X ¹
MRD Testing	X ²						
Response Assessment	n/a						X
Study Drug Diaries	n/a	X				X ⁵	

Adverse Events ⁷	n/a	X	X	X		X	X
-----------------------------	-----	---	---	---	--	---	---

1. Bone marrow aspirate and biopsy will be done at screening and on cycle 2 day 1, and to confirm CR after 4 cycles, 8 cycles and as indicated and at time of PD for lab correlative studies as outlined in page 26. In parallel a peripheral blood sample will be collected for lab correlative studies at same time points and on day 1 of each cycle. Bone marrow aspirates (30mL volume) for correlative studies will be collected at baseline, Cycle 2 day 1, and thereafter for confirmation of CR, and at time of disease progression to analyze marrow-infiltrating immune populations by MPFC. In parallel, PBMCs, isolated from 20-30mL freshly drawn sample, will be analyzed similarly at 4-week intervals corresponding to Day 1 of each cycle as well as at time of progression.
2. MRD testing will be performed at screening, by flow cytometry and NSG on patients and as indicated on patients in hematologic complete remission. An aliquot of serum will be stored for those patients with IgG MM who achieved VGPR to evaluate extent of interference by the antibody therapy.
3. Bone survey will be done at screening and once yearly or when clinically indicated. May be substituted by PET scan or MRI as clinically indicated
4. Response assessment will be done every 2 cycles.
5. Study drug diaries will be collected after each cycle
6. Will only capture in CRF if related to adverse event.
7. All females of childbearing potential should complete a serum pregnancy test within 7 days prior to the administration of Elotuzumab and lenalidomide on day 1 of cycle 1. The pregnancy test should be repeated in week 1 of every cycle (except for cycle 1). Postmenopausal women must have been amenorrheic for ≥ 12 months in order to be considered "of non-childbearing potential".
8. Only grade > 2 adverse events possibly related to study drug will be captured in CRF
9. For patients with urine M spike of less than 200 mg/24 hours at screening, 24-hour urine collection with UPEP will be done every other cycle)

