	Hematology (CBC) (within 28 days of therapy) Clinical chemistry (within 28 days of therapy) Assessment of disease status (within 28 days of therapy) (SPEP, 24h UPEP, serum free light chain) Bone marrow aspiration and biopsy with cytogenetics, FISH, My PRS (gene expression profile) (within 28 days of therapy) Skeletal survey (within 28 days of therapy) Concomitant medication
Treatment and post treatment assessments	Day 1 of each cycle Physical examination and vital signs CBC (also day 8, 15, 22 of cycles 1-2) Complete clinical chemistry (also day 8, 15, 22 of cycles 1-2) Assessment of disease status (SPEP, 24h UPEP, Quantitative Immunoglobulins, serum free light chain) Adverse events and concomitant medication Pregnancy test if applicable
Response	Response will be assessed per the uniform response criteria of the IMWG
Safety variables and analysis	The safety and tolerability of Elotuzumab and lenalidomide given for the treatment of serologic progression after first line therapy to myeloma patients will be evaluated by means of AE reports, physical examinations, and laboratory safety evaluations. Common Terminology Criteria for Adverse Events (CTCAE) V 5.0 will be used for grading of AEs. Investigators will provide their assessment of causality as 1) unrelated, 2) unlikely related, 3) possibly related, or 4) probably or 5) definitely related for all AEs to one both study drugs.

Table of Contents

1.1 Overview and Study Rationale	13
1.2 Overview of Elotuzumab	14
1.2.1 Combination studies of Lenalidomide and elotuzumab	15
2 Study objectives	16
2.1 Primary Objective	16
2.2 Secondary Objectives	16
3 Overall study design	16
4 Study population	18
4.1 Inclusion criteria	18
4.2 Exclusion criteria	19
5 Treatments	20
5.1 Investigational therapy	20
5.2 Treatment cycle and duration	21
5.6 Interruption or discontinuation of treatment	23
5.7 Dose modifications for elotuzumab	23
5.8 Dose modifications for lenalidomide-related toxicity	23
5.9 Study drug discontinuation	24
5.10 Other concomitant medications	25
5.11 Treatment compliance	26
6 Visit schedule and assessments	26
6.1 Visit schedule	26
6.2 Efficacy assessments	28
6.3 Safety assessments	28
6.3.1 Adverse events	29
6.3.2 Vital signs	29
6.3.3 Physical examination	30
6.3.4 Laboratory evaluations	30
7 Statistical methods	32
7.1 Primary Efficacy Analysis	32
7.2 Secondary Endpoints Analyses	33
8 REGULATORY CONSIDERATIONS	33
8.1 Institutional Review Board/Ethics Committee Approval	33
8.2 Informed Consent	33

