6.3 Safety assessments

Safety assessments will consist of monitoring and recording all adverse events and serious adverse events, the regular monitoring of hematology, blood chemistry, vital signs, ECOG performance status, and the regular physical examinations .

Adverse events will be assessed according to the Common Toxicity Criteria for Adverse Events (CTCAE) version 5.0. This can be accessed on the NIH/NCI website at:

(http://ctep.cancer.gov/protocolDevelopment/electronic_applications/docs/ctcaev5.pdf)

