6.3.1 Adverse events

Information about all adverse events, whether volunteered by the subject, discovered by investigator questioning, or detected through physical examination, laboratory test or other means, will be collected and recorded and followed as appropriate. Adverse events will be collected from cycle 1, day 1, and while the patients are on study treatment only.

An adverse event is the appearance or worsening of any undesirable sign, symptom, or medical condition occurring after starting the study drug even if the event is not considered to be related to study drug. Medical conditions/diseases present before starting study drug are only considered adverse events if they worsen after starting study drug. Abnormal laboratory values or test results constitute adverse events only if they induce clinical signs or symptoms, are considered clinically significant, or require therapy.

The occurrence of adverse events should be sought by non-directive questioning of the patient at each visit during the study. Adverse events also may be detected when they are volunteered by the patient during or between visits or through physical examination, laboratory test, or other assessments. As far as possible, each adverse event should be evaluated to determine:

1. the severity grade (mild, moderate, severe) or (grade 1-4)
2. its relationship to the study drug(s) (suspected/not suspected)
3. its duration (start and end dates or if continuing at final exam)
4. action taken (no action taken; study drug dosage adjusted/temporarily interrupted; study drug permanently discontinued due to this adverse event; concomitant medication taken; non-drug therapy given; hospitalization/prolonged hospitalization)
5. whether it constitutes a serious adverse event (SAE)

All adverse events should be treated appropriately. Such treatment may include changes in study drug treatment including possible interruption or discontinuation, starting or stopping concomitant treatments, changes in the frequency or nature of assessments, hospitalization, or any other medically required intervention. Once an adverse event is detected, it should be followed until its resolution, and assessment should be made at each visit (or more frequently, if necessary) of any changes in severity, the suspected relationship to the study drug, the interventions required to treat it, and the outcome.

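### Table 6-1 keeps blood counts and chemistry out of the CRF unless tied to an adverse event, so a complete laboratory toxicity summary by cohort cannot be built from CRF data

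*Combined protocol and SAP*

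**What the plan says.** The visit schedule (section 6.1, Table 6-1) attaches marker 6 to the row "Vital signs, Physical examination and ECOG Performance Score ⁶", to concomitant medications, to CBC with differential, and to the row "CMP ⁶ ,Pregnancy Test ⁶". The text of footnote 6 is: "Will only capture in CRF if related to adverse event".

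The synopsis, under safety variables and analysis, states that safety and tolerability "will be evaluated by means of AE reports, physical examinations, and laboratory safety evaluations". Section 6.3 likewise names, in addition to adverse event recording, "the regular monitoring of hematology, blood chemistry, vital signs, ECOG performance status, and the regular physical examinations".

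Section 6.3.1 sets the bar for a laboratory finding: "Abnormal laboratory values or test results constitute adverse events only if they induce clinical signs or symptoms", or are judged clinically significant, or need therapy. It also starts adverse event collection at cycle 1, day 1.

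The documents give two thresholds for entering adverse events in the CRF. Table 6-1 footnote 8 and section 6.3.1 restrict entry to events above grade 2 that are possibly drug-related. Section 9.3 restricts it to events above grade 1 and says nothing about relatedness.

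Section 7 contains no safety or laboratory analysis.

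**The concern.** The capture rule selects on outcome: a laboratory value is kept only once someone has connected it with an adverse event. For a patient with no such event, the dataset cannot distinguish a normal course from an abnormal one that was not reported. Rates of laboratory toxicity from such data have a numerator that depends on reporting behaviour and no measured values behind the denominator.

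This matters here for three reasons:

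- Among the grade 3/4 events the protocol cites for elotuzumab with lenalidomide and dexamethasone, the differences it highlights are laboratory ones. The synopsis gives lymphopenia at 77% versus 49% (section 1.3.1 has 78% versus 49%). Lymphopenia without symptoms or treatment is the kind of finding that section 6.3.1 leaves to judgement.
- The two cohorts differ only in lenalidomide dose, and section 5.8 ties lenalidomide modifications to platelet and neutrophil counts. A reader of the trial report will want those counts by cohort.
- Elotuzumab is listed as open label in section 5.1, and no blinding of the lenalidomide dose is described. Judgements of clinical significance are therefore made with the cohort known.

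**Working it through.** The plan gives no figure to reproduce, so the check is mainly textual, with one count for scale.

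**1. Does footnote 6 govern these rows?** The later markers in Table 6-1 are misaligned with their texts. The pregnancy test is marked 6 but its text is footnote 7. Adverse events are marked 7 but the text is footnote 8. UPEP is marked 8 but the text is footnote 9. Markers 1, 2, 3 and 5 match their texts. The pattern fits a footnote 6 that was inserted without renumbering what follows. If marker 6 were read everywhere as footnote 7, the pregnancy-test text would apply to blood counts, vital signs and concomitant medications, which makes no sense. Footnote 6 is the only text that fits those rows.

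**2. What passes the filters?**

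| Type of laboratory result | Route into the CRF |
|---|---|
| Screening, before cycle 1 day 1 | No adverse event is collected yet, so on a literal reading nothing qualifies |
| Abnormal, with symptoms or needing therapy | An adverse event by definition, then subject to the grade and relatedness threshold |
| ANC below 0.75 x 10^9/L | Section 5.8 directs growth factor, so it needs therapy and is an adverse event by rule |
| Abnormal, no symptoms, no therapy (for example lymphopenia, or neutropenia above that ANC level) | An adverse event only if the investigator calls it clinically significant |
| Normal | None |

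**3. What can be tabulated?** Adverse events with a laboratory basis can be tabulated by cohort, subject to whichever threshold applies. Grade 2 events, for example, are excluded under section 6.3.1 and included under section 9.3. Worst CTCAE laboratory grade over all treated patients, and shift from baseline, cannot: both need the unselected values, and the second also needs screening results.

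**4. Scale.** Scheduled CBC/CMP panels per patient, from Table 6-1 and the synopsis schedule, are 1 at screening, 4 in each of cycles 1 and 2, 1 in each later cycle, and 1 at end of study.

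- 6 cycles: 1 + 8 + 4 + 1 = 14 panels; 14 x 60 = 840.
- 12 cycles: 1 + 8 + 10 + 1 = 20 panels; 20 x 60 = 1,200.

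These are panels scheduled if all 60 patients complete that many cycles, not panels lost. The documents do not allow an estimate of the share linked to an adverse event.

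**5. Is efficacy touched?** The SPEP/UPEP/immunofixation and free light chain rows do not carry marker 6. Hemoglobin, calcium and creatinine enter the definition of clinical relapse, but the synopsis and Appendix B both state that clinical relapse is not used to calculate PFS or time to progression.

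**The case against.** The strongest defence is that restricting CRF entry to event-related laboratory values is a deliberate economy in a phase 2 trial with PFS as its primary endpoint and commercially available drugs. Footnote 6 limits data entry, not testing. Section 6.3.4 requires results to be reviewed before elotuzumab is given, section 9.3 requires every abnormal result to be appraised, section 5.6 requires dose interruptions and changes to be recorded, and section 8.4 requires source records to be retained. The most severe neutropenia is an adverse event by rule. All of this stands, and it limits the point to milder or untreated abnormalities and to baseline values.

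It also rules out several stronger conclusions that a reader might draw:

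- *That laboratory safety cannot be evaluated at all.* Event-linked values are captured and the rest could be retrieved from source, although that would be unplanned work.
- *That a planned laboratory comparison of 25 mg with 10 mg is defeated.* No such comparison is planned. The synopsis speaks of the combination as a whole, the cohort comparison in section 7.2 names only clinical outcomes, and section 7 calls comparative analyses exploratory.
- *That cytopenia is the expected difference between the lenalidomide doses.* The documents do not say so. The cited cytopenia rates compare treatment with and without elotuzumab.
- *That the primary endpoint is damaged.* Step 5 of the working shows why it is not.

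The defence does not answer the mismatch between footnote 6 and the synopsis, which lists laboratory evaluation as a component separate from adverse event reports.

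**Conclusion.** The concern holds in this limited form. Under footnote 6, a complete and unselected laboratory toxicity summary by cohort cannot be made from the CRF, although the synopsis and section 6.3 treat laboratory evaluation as a component of safety in its own right. Laboratory abnormalities without symptoms or treatment enter the dataset only on investigator judgement in an open-label trial, and no systematic baseline is captured. PFS and response are not affected.

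This rests on reading marker 6 on the CBC, CMP and vital signs/ECOG rows as footnote 6 despite the misnumbering, and on the CRF being the source of the analysis dataset. The values exist and are already scheduled, about 840 to 1,200 panels under the completion assumption above, so the gap can be closed cheaply. It is an improvement worth making and does not invalidate the design.

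**What to change.** 1. Remove footnote 6 from the CBC and CMP rows, and from ECOG if wanted. Enter or electronically transfer all scheduled results for every patient, including screening.
2. Add to section 7 a descriptive tabulation by cohort of worst CTCAE laboratory grade and shift from baseline, derived from the values. No test between cohorts is needed.
3. Renumber the Table 6-1 markers so that the pregnancy test, adverse event and UPEP rows point to their own footnotes.
4. Reconcile the adverse event capture thresholds in Table 6-1 footnote 8 and section 6.3.1 with the one in section 9.3.

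If the sponsor prefers to keep footnote 6, the synopsis and section 6.3 should say plainly that laboratory safety rests on adverse event reports alone. That removes the contradiction but not the selective recording.

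The cost is data management for roughly 840 to 1,200 panels if all 60 patients complete 6 to 12 cycles. It is less if patients stop earlier and more for any who continue beyond 12 cycles. No additional blood draw, visit or change of treatment is involved.

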6.2 Efficacy assessments

Response will be determined by the investigator based on the disease assessments described above and the IMWG-URC (see definitions in [Appendix B](#)). Myeloma response will be assessed at the beginning of each cycle.

The following confirmatory assessments are required for all response categories (stringent complete response [sCR], CR, VGPR, and PR) and progressive disease:

- All laboratory-based progressive disease and all responses require 2 consecutive assessments made at any time before initiation of any new therapy. Confirmatory lab samples should be separated by at least 1 calendar day
- Progressive disease by nonlaboratory-based assessment (i.e.; plasmacytoma or skeletal lesion) does not require confirmatory report
- All response categories also require no evidence of progression including new bone lesions if radiographic studies were performed
- Confirmation of CR or sCR requires bone marrow biopsy or aspirate slides (a confirmatory bone marrow sample is not required)
- Extramedullary plasmacytoma evaluation (if present at baseline)

6.3 Safety assessments

Safety assessments will consist of monitoring and recording all adverse events and serious adverse events, the regular monitoring of hematology, blood chemistry, vital signs, ECOG performance status, and the regular physical examinations .

Adverse events will be assessed according to the Common Toxicity Criteria for Adverse Events (CTCAE) version 5.0. This can be accessed on the NIH/NCI website at:

(http://ctep.cancer.gov/protocolDevelopment/electronic_applications/docs/ctcaev5.pdf)

6.3.1 Adverse events

Information about all adverse events, whether volunteered by the subject, discovered by investigator questioning, or detected through physical examination, laboratory test or other means, will be collected and recorded and followed as appropriate. Adverse events will be collected from cycle 1, day 1, and while the patients are on study treatment only.

An adverse event is the appearance or worsening of any undesirable sign, symptom, or medical condition occurring after starting the study drug even if the event is not considered to be related to study drug. Medical conditions/diseases present before starting study drug are only considered adverse events if they worsen after starting study drug. Abnormal laboratory values or test results constitute adverse events only if they induce clinical signs or symptoms, are considered clinically significant, or require therapy.

The occurrence of adverse events should be sought by non-directive questioning of the patient at each visit during the study. Adverse events also may be detected when they are volunteered by the patient during or between visits or through physical examination, laboratory test, or other assessments. As far as possible, each adverse event should be evaluated to determine:

1. the severity grade (mild, moderate, severe) or (grade 1-4)
2. its relationship to the study drug(s) (suspected/not suspected)
3. its duration (start and end dates or if continuing at final exam)
4. action taken (no action taken; study drug dosage adjusted/temporarily interrupted; study drug permanently discontinued due to this adverse event; concomitant medication taken; non-drug therapy given; hospitalization/prolonged hospitalization)
5. whether it constitutes a serious adverse event (SAE)

All adverse events should be treated appropriately. Such treatment may include changes in study drug treatment including possible interruption or discontinuation, starting or stopping concomitant treatments, changes in the frequency or nature of assessments, hospitalization, or any other medically required intervention. Once an adverse event is detected, it should be followed until its resolution, and assessment should be made at each visit (or more frequently, if necessary) of any changes in severity, the suspected relationship to the study drug, the interventions required to treat it, and the outcome.

Information about common side effects already known about the investigational drug can be found in the [\[Investigators' Brochure\]](#) or will be communicated between IB updates in the form of Investigator Notifications. This information will be included in the patient informed consent and should be discussed with the patient during the study as needed.

Only grade > 2 adverse events possibly related to study drug will be captured in CRF Adverse events will NOT be collected under following circumstances:

1. Grade 1 unrelated adverse events
2. During screening phase or before cycle 1, day 1 of treatment

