9.3 Adverse Drug Reporting

Toxicity will be scored using CTCAE Version 5.0 for toxicity and adverse event reporting. A copy of the CTCAE Version 5.0 can be downloaded from the CTEP homepage (<http://ctep.info.nih.gov>). All appropriate treatment areas should have access to a copy of the CTCAE Version 5.0. All adverse clinical experiences, whether observed by the investigator or reported by the patient, must be recorded, with details about the duration and intensity of each episode, the action taken with respect to the test drug, and the patient’s outcome. The investigator must evaluate each adverse experience for its relationship to the test drug and for its seriousness. Note that only adverse events that are greater than grade 1 will be captured in the case report forms and reported.

The investigator must appraise all abnormal laboratory results for their clinical significance. If any abnormal laboratory result is considered clinically significant, the investigator must provide details about the action taken with respect to the test drug and about the patient’s outcome.

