9.4 Investigator Reporting Responsibilities

9.4.1 Reporting to FDA

The conduct of the study will comply with all FDA safety reporting requirements.

IND Annual Reports

If the FDA has granted an IND number, it is a requirement of 21 CFR 312.33, that an annual report is provided to the FDA within 60-days of the IND anniversary date. 21 CFR 312.33 provides the data elements that are to be submitted in the report.

Serious adverse events will be forwarded to FDA by the Sponsor-Investigator according to 21 CFR 312.32.

It is the responsibility of the PI and the research team to ensure serious adverse events are reported according to the Code of Federal Regulations, Good Clinical Practices, the protocol guidelines, the sponsor's guidelines, and Institutional Review Board policy.

All adverse experience reports must include the patient number, age, sex, weight, severity of reaction (mild, moderate, severe), relationship to study drug (probably related, unknown relationship, definitely not related), date and time of administration of test medications and all concomitant medications, and medical treatment provided. The investigator is responsible for evaluating all adverse events to determine whether criteria for "serious" and as defined above are present.

Adverse drug reactions that are Serious, Unlisted/unexpected, and at least possibly associated to the drug, and that have not previously been reported in the Investigators brochure, or reference safety information document should be reported promptly to the Food and Drug Administration (FDA) in writing by each investigator/physician engaged in clinical research. A clear description of the suspected reaction should be provided along with an assessment as to whether the event is drug or disease related.

The investigator/physician shall notify the FDA by telephone or by fax of any unexpected fatal or life threatening experience associated with the use of the drug. As soon as possible, but no later than 7 calendar days after the sponsors initial receipt of the information. Each phone call or fax shall be transmitted to the FDA new drug review division in the Center for Drug Evaluation and Research or the product review division in the Center for Biologics Evaluation and Research that has responsibility for review of the IND if applicable.

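### Section 6.3.1 and section 9.3 set different rules for which adverse events enter the case report form, and nothing says which governs

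*Combined protocol and SAP*

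**What the plan says.** Three places state what goes into the case report form (CRF).

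- Section 6.3.1 says "Only grade > 2 adverse events possibly related to study drug will be captured in CRF". Footnote 8 to Table 6-1 repeats the sentence.
- Section 9.3 says that "only adverse events that are greater than grade 1 will be captured in the case report forms and reported". It sets no condition on relationship to study drug.

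Directly after its CRF sentence, section 6.3.1 gives a list introduced by "Adverse events will NOT be collected under following circumstances". Item 1 is "Grade 1 unrelated adverse events"; item 2 is a timing exclusion covering everything before Cycle 1 Day 1.

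On attribution, the synopsis (Safety variables and analysis) says "Investigators will provide their assessment of causality as 1) unrelated, 2) unlikely related" and continues to five levels, for all adverse events. Section 6.3.1 uses a suspected/not suspected split, and section 9.4.1 uses a three-level scale for the content of adverse experience reports.

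On the time window, section 6.3.1 says "Adverse events will be collected from cycle 1, day 1, and while the patients are on study treatment only", while section 5.9.1.1 has all patients followed for adverse events for no less than 4 weeks after the final dose. Serious adverse events (SAEs) have their own route: sections 9.1 and 9.4.2 require them to be reported whatever their relationship to treatment, and section 9.4.2 runs from consent to 30 days after dosing stops.

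**The concern.** The synopsis says that safety and tolerability will be evaluated partly from adverse event reports, and the Protocol Monitoring Committee in section 10.2 reviews safety data. Both depend on what is in the CRF.

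Under the section 6.3.1 rule, non-serious grade 2 events, and non-serious grade 3 and 4 events judged unrelated, would not be there. Entry would also turn on the investigator's attribution in a randomised comparison of lenalidomide 25 mg with 10 mg, where elotuzumab is listed as open label and no blinding of the lenalidomide dose is described. Under the section 9.3 rule the same events would be entered. Staff who follow different sections would therefore build different data sets, and an event that was never entered cannot later be tabulated from the CRF.

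**Working it through.** There is no planned figure to reproduce. The check sets the rules side by side.

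**Inputs.** Grades 1 to 4 come from the severity item in section 6.3.1. Attribution is split in two, reading the filter term as at least possibly related. Only non-serious events are counted, because SAEs are reported separately under sections 9.1 and 9.4.2; grade 5 drops out because section 9.2 makes any death serious. This gives 4 × 2 = 8 categories.

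| Non-serious event | Footnote 8 and section 6.3.1 | Section 9.3 | Same answer? | Left in by the 6.3.1 list |
|---|---|---|---|---|
| Grade 1, related | out | out | yes | yes |
| Grade 1, unrelated | out | out | yes | no |
| Grade 2, related | out | in | **no** | yes |
| Grade 2, unrelated | out | in | **no** | yes |
| Grade 3, related | in | in | yes | yes |
| Grade 3, unrelated | out | in | **no** | yes |
| Grade 4, related | in | in | yes | yes |
| Grade 4, unrelated | out | in | **no** | yes |

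**Result.** The narrow rule admits 2 categories and section 9.3 admits 6. The 2 lie inside the 6, so the rules disagree on 6 − 2 = 4 of 8.

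**Could it be a slip for grade 2 or higher?** The narrow rule would then admit 3 categories (grades 2, 3 and 4, related), and 6 − 3 = 3 would still be in conflict: grades 2, 3 and 4, unrelated. Correcting the inequality sign leaves the attribution conflict in place.

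**Supporting evidence.** The exclusion list leaves 7 of 8 categories in. If it governed the CRF, grade 1 related events would also be in dispute, making 4 + 1 = 5. Its verb is collected, not captured, so this is not counted in the main result.

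**Limit.** These are counts of categories, not of events. The documents give no event rates by grade and attribution for this regimen.

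**The case against.** The best defence is that both statements begin with a restriction and so can both be true: if the narrow rule applies, nothing of grade 1 is captured either. That works as logic, but section 9.3 would then misdescribe what is captured and reported, and neither section points to the other. The conflict stands.

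Other objections succeed and limit the point.

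- A reader might infer a three-way contradiction from the exclusion list. The documents do not establish it. Sections 6.3.1 and 9.3 also say that all events are recorded, so the list may describe source records, with the CRF as a narrower subset.
- A reader might infer that the attribution filter cannot be applied because three scales are in use. The synopsis requires its five-level scale, which contains a possibly related level, for every adverse event, so the filter can be applied. The section 9.4.1 scale concerns report content. The mixture is untidy, not unworkable.
- A reader might see a firm contradiction on the end of collection. Section 5.9.1.1 may mean clinical follow-up; it does not say.
- The category count depends on the partition chosen. It shows where the rules part, not how much data is at risk.

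It is also true that section 2 lists no safety objective and section 7 specifies no adverse event analysis. The synopsis does plan a safety evaluation, so the CRF rule still matters.

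**Conclusion.** Footnote 8 and section 6.3.1 conflict with section 9.3 on both grade and attribution for the same forms, and the protocol does not say which prevails. For non-serious events the conflict covers grade 2, related or not, and unrelated grades 3 and 4. This rests on reading the filter as at least possibly related and on leaving SAEs to their own route. The number of events cannot be given.

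The consequence is confined to the safety description. A reader might infer that serious toxicity could go unseen or that the primary result is at risk; neither follows. SAEs are reported regardless of attribution, changes to study drug administration (section 5.6) and reasons for discontinuation (section 5.9) are recorded, and neither progression-free survival nor power uses these data. What is not protected is a non-serious event that led to no change in treatment. The text should be corrected; this is not a flaw in the design.

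**What to change.** State one CRF rule in footnote 8, section 6.3.1 and section 9.3. The preferable rule is the protocol's own section 9.3 threshold, because it needs no attribution judgement at entry: all adverse events of grade 2 or higher regardless of attribution, plus SAEs of any grade. Record attribution as a variable on the synopsis five-level scale. If the sponsor prefers a narrower CRF, the three places must still agree on grade, attribution, and source record versus CRF.

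Align both items of the section 6.3.1 list. Item 1 should exclude only non-serious grade 1 events. Item 2 should not exclude SAEs, which section 9.4.2 collects from consent.

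Separately, reconcile sections 6.3.1 and 5.9.1.1 on when adverse event collection ends. Ending at 30 days after the last dose would match section 9.4.2 and meet the 4-week (28-day) minimum. It may need a post-treatment contact: Table 6-1 has an End of Study column but does not date it relative to the last dose.

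The cost is more CRF entries for 60 patients treated until progression, including the linked items that footnote 6 enters only when they relate to an adverse event. The documents give no basis for estimating how many. The change is also a protocol amendment, which under section 11.1 needs review and approval by the company supplying elotuzumab and approval by the IRB or ethics committee.
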